### Table 60: ECG Toxicity Grade by Parameter, Timepoint, and Severity – Safety Subset Population

				Measu	rement			Change	from Pre-Dos	e Baseline	
Parameter	Timepoint	Ν	Mean	SD	Median	Min, Max	Mean	SD	Median	Min, Max	90% CI
PR Interval (msec)	Baseline	х	XX.X	XX.X	XX.X	xx, xx	-	-	-	-	-
	Day 1, 1 h Post-Dose	x	XX.X	XX.X	XX.X	xx, xx	XX.X	XX.X	XX.X	xx, xx	(xx.x, xx.x)
	Day 1, 4 h Post-Dose	х	XX.X	XX.X	XX.X	xx, xx	XX.X	XX.X	XX.X	xx, xx	(xx.x, xx.x)
	Day 1, 16 h Post-Dose	x	XX.X	XX.X	XX.X	xx, xx	XX.X	XX.X	XX.X	xx, xx	(xx.x, xx.x)
	Day 2, 24 h Post-Dose	x	XX.X	XX.X	XX.X	xx, xx	XX.X	XX.X	XX.X	xx, xx	(xx.x, xx.x)
	Day 2, 36 h Post-Dose	x	XX.X	XX.X	XX.X	xx, xx	XX.X	XX.X	XX.X	xx, xx	(xx.x, xx.x)
	Day 3, 48 h Post-Dose	x	XX.X	XX.X	XX.X	xx, xx	XX.X	XX.X	XX.X	xx, xx	(xx.x, xx.x)
	Day 3, 60 h Post-Dose	x	XX.X	XX.X	XX.X	xx, xx	XX.X	XX.X	XX.X	xx, xx	(xx.x, xx.x)
	Day 14	x	XX.X	XX.X	XX.X	xx, xx	XX.X	XX.X	XX.X	xx, xx	(xx.x, xx.x)
QRS Duration (msec)	Baseline	x	XX.X	XX.X	XX.X	xx, xx	-	-	-	-	-
	Day 1, 1 h Post-Dose	x	XX.X	XX.X	XX.X	xx, xx	XX.X	XX.X	XX.X	xx, xx	(xx.x, xx.x)
		x	XX.X	XX.X	XX.X	xx, xx	XX.X	XX.X	XX.X	xx, xx	(xx.x, xx.x)
		x	XX.X	XX.X	XX.X	xx, xx	XX.X	XX.X	XX.X	xx, xx	(xx.x, xx.x)
Notes: N = Number of pa	articipants in the Safety Populat	ion with the	ECG measuren	nent assessed at	the respective	timepoint. Pre-I	Dose Baseline	= The most rec	ent measureme	ent prior to star	t of infusion.

### Table 61: ECG Measurement and Change from Pre-Dose Baseline by Parameter and Timepoint – Safety Population

Table with similar format:

### Table 62: ECG Measurement and Change from Pre-Dose Baseline by Parameter and Timepoint – Safety Subset Population

		Study			Measu	rement			Change from	m Time-Match	ed Baseline	
Parameter	Timepoint	Day	Ν	Mean	SD	Median	Min, Max	Mean	SD	Median	Min, Max	90% CI
PR Interval (msec)	1 h Post-Dose	Baseline	х	XX.X	XX.X	XX.X	xx, xx	-	-	-	-	-
		Day 1	x	XX.X	XX.X	XX.X	xx, xx	XX.X	XX.X	XX.X	xx, xx	(xx.x, xx.x)
	4 h Post-Dose	Baseline	x	XX.X	XX.X	XX.X	xx, xx	-	-	-	-	-
		Day 1	x	XX.X	XX.X	XX.X	xx, xx	XX.X	XX.X	XX.X	xx, xx	(xx.x, xx.x)
	16 h Post-Dose	Baseline	x	XX.X	XX.X	XX.X	xx, xx	-	-	-	-	-
		Day 1	x	XX.X	XX.X	XX.X	xx, xx	XX.X	XX.X	XX.X	xx, xx	(xx.x, xx.x)
QRS Duration (msec)	1 h Post-Dose	Baseline	x	XX.X	XX.X	XX.X	xx, xx	-	-	-	-	-
		Day 1	x	XX.X	XX.X	XX.X	xx, xx	XX.X	XX.X	XX.X	xx, xx	(xx.x, xx.x)
			х	XX.X	XX.X	XX.X	xx, xx	XX.X	XX.X	XX.X	xx, xx	(xx.x, xx.x)
Notes: $N = Number of$	participants in the	Safety Popula	tion with th	e ECG measure	ement assessed	at the respectiv	e timenoint Tir	ne-Matched Ba	seline = The m	easurements re	corded on Day	-1

### Table 63: ECG Change from Time-Matched Baseline by Parameter and Timepoint – Safety Population

Table with similar format:

### Table 64: ECG Change from Time-Matched Baseline by Parameter and Timepoint – Safety Subset Population

			ategory							
		QTcF >450 - 480 msec	QTcF >480 - 500 msec	QTcF >500 msec	QTcF increase ≥30 – 59 msec from baseline	QTcF increase ≥60 msec from baseline				
Timepoint	Ν	n (%)	n (%)	n (%)	n (%)	n (%)				
Day 1, 1 h Post-Dose	х	x (xx)	x (xx)	x (xx)	x (xx)	x (xx)				
Day 1, 4 h Post-Dose	x	x (xx)	x (xx)	x (xx)	x (xx)	x (xx)				
Day 1, 16 h Post-Dose	х	x (xx)	x (xx)	x (xx)	x (xx)	x (xx)				
Day 2, 24 h Post-Dose	x	x (xx)	x (xx)	x (xx)	x (xx)	x (xx)				
Day 2, 36 h Post-Dose	х	x (xx)	x (xx)	x (xx)	x (xx)	x (xx)				
Day 3, 48 h Post-Dose	х	x (xx)	x (xx)	x (xx)	x (xx)	x (xx)				
Day 3, 60 h Post-Dose	х	x (xx)	x (xx)	x (xx)	x (xx)	x (xx)				
Day 14	х	x (xx)	x (xx)	x (xx)	x (xx)	x (xx)				
Notes: $N = Number of participants in the Safety Population with the ECG measurement assessed at the respective timepoint. n = Number of participants who experienced the event. A participant may be counted in more than one category. Pre-Dose Baseline = The most recent measurement prior to start of infusion.$										

 Table 65:
 Categorical Summary of QTcF Interval by Timepoint – Safety Population

Table with similar format:

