### 8.1.7 12-lead Standard Electrocardiogram (ECG)

Single 12-lead standard ECG and 10-sec rhythm strip will be obtained at the Screening Visit, on Day -2, at  $24 \pm 1$  h and  $36 \pm 1$  h (Day 2) and 48 h  $\pm 1$  h and 60 h  $\pm 1$  h (Day 3) after dosing, and on Day 14 ( $\pm 3$  days), or ET.

Triplicate 12-lead standard ECGs will be obtained over a period of 5 minutes on Day -1 (at the same 4 timepoints as projected to be taken on Day 1), and on Day 1 pre-dose (within 30 min) and at 1 h  $\pm$ 5 min, 4 h  $\pm$ 10 min and 16 h  $\pm$  15 min after dosing.

ECGs will be performed after the subject rests quietly in a supine position for at least 5 min. The ECGs will be reviewed by the PI or a designated clinician (listed on FDA Form 1572). ECGs will be analyzed for PR, QRS and QT intervals, ventricular rate (based on RR intervals), and for morphological abnormalities. The QT interval will be corrected by the Fridericia (QTcF) formula, recorded and analyzed. To be eligible for participation, the QTcF interval must be within protocol reference range criteria at Screening and Day -2 and there must be no clinically significant ECG abnormalities after enrollment on Day -1 and before dosing on Day 1. If the site PI identifies clinically significant changes in the ECGs after enrollment in Day -1 and before dosing on Day 1, the subject would not be eligible to receive study drug and should be withdrawn and replaced. ECG PR and QTcF intervals after dosing will be reported as TEAEs if they meet toxicity grading criteria (See Appendix B, Table 4). If a question regarding ECG interpretation arises, the study investigators will have the ECG reviewed by a cardiologist.

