#### 11.4.6.2 Categorical Analyses

QTcF intervals will be categorized and tabulated for each treatment. The following criteria will be used to specify noteworthy QTcF intervals:

- QTcF >450 msec
- QTcF >480 msec
- QTcF >500 msec
- QTcF increase  $\geq$  30 msec from baseline
- QTcF increase  $\geq 60$  msec from baseline

Categorical analysis of PR, QRS, and RR intervals will also be performed. The following criteria will be used to specify noteworthy non-QTc intervals (PR, QRS, and RR intervals) and HR:

- PR change-from-baseline >25% resulting in PR >200 msec
- QRS change-from-baseline >25% resulting in QRS >120 msec
- HR change-from-baseline >25% decrease resulting in HR <50 bpm

DMID Protocol 20-0012	Version 5.0
Apramycin	10 July 2023

• HR change-from-baseline >25% increase resulting in HR >100 bpm

The number and percent of subjects in each category will be calculated. Comparisons across timepoints may be conducted if sufficient counts are observed.

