- 12-lead standard ECG
  - ECG will be performed in either triplicate or single at Screening, Check-In (Day -2), Day -1 (at timepoints matching those on Day 1), Day 1 (pre-dose and 1 h, 4 h, and 16 h post-dose), Day 2 (24 h and 36 h post-dose), Day 3 (48 h and 60 h post-dose), and Day 14.
    - For ECG measurements performed in triplicate, the mean of the replicates will be used for analysis, including analyses of change from baseline.
  - At each timepoint, the overall interpretation of the ECG will be reported as Normal; Abnormal, Not Clinically Significant (NCS); or Abnormal, Clinically Significant (CS). For post-dose timepoints, the change from baseline will be also reported as No change from baseline; NCS, change from baseline; or CS, change from baseline.
  - The following parameters will be measured: PR interval, QRS interval, QT interval, corrected QT interval using Fridericia's Formula (QTcF correction), RR internal, and ventricular rate.
    - For replicate ECGs recorded on Day -1 and Day 1, the mean time-matched change-frombaseline QTcF values (ΔΔQTcF) will be evaluated to quantify the QTcF prolongation. For single ECG recoded after dosing, the mean pre-dose change-from-baseline (ΔQTcF) will also be analyzed.
- Audiology
  - The following audiology tests will be conducted:
    - Valsalva test, Tympanometry and Stapedial Reflexes at Screening only.
    - Ear otoscopy at Screening, Check-In (Day -2), Day 3, Day 14, and Day 30.

- Pure tone audiometry at standard frequencies (0.5 to 8.0 kHz) at Screening and at both standard and higher frequencies (9.0 to 20.0 kHz) at Check-In (Day -2), Day 3, Day 14, and Day 30.
- DPOAEs (1.5 to 6.0 kHz) at Screening, Check-In (Day -2), Day 3, Day 14, and Day 30.
- Physical Examination
  - A complete PE to assess general appearance; head, eyes, ears, nose, and throat (HEENT); heart, lungs, abdomen, skin, musculoskeletal system, and lymph nodes; and a neurological exam will be performed at Screening, Check-In (Day -2), Day 3 (60 h post-dose), and Day 14.
  - An abbreviated PE will be performed at Day -1. An abbreviated PE differs from a complete PE in that the abdomen and neurological system are not evaluated.
  - A symptom-directed (focused) PE may be performed on Day 1 and at any time after dosing for evaluation of TEAEs.
  - Height and weight will be measured, and BMI calculated, at Screening only. Weight only will be measured on Day -2 and Day 14.

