#### 12.4.1 Individual Laboratory Measurements and Abnormal Laboratory Values

#### Table 4: Clinical Laboratory Reference Ranges and Toxicity Grading Scales (Continued)

#### Table 6:ECG Toxicity Grading Scale

ECG interval abnormality	Reference range	Grade 1	Grade 2	Grade 3
QTcF interval prolonged (msec): • Male • Female	• ≤450 msec • ≤470 msec	Asymptomatic, QTcF • 451 - 479 msec • 471 - 479 msec	Asymptomatic, QTcF 480-500 msec OR increase in interval 30-59 msec above baseline	Asymptomatic, QTcF >500 msec OR increase in interval ≥60 msec above baseline
PR interval prolonged (msec)	≤210 msec	211-250 msec	>250 msec	Type II 2 nd degree AV block OR ventricular pause >3.0 sec

Note 1: Events will be coded as treatment-emergent SAEs if there are life-threatening associated symptoms or signs (arrhythmia, CHF, hypotension, syncope, TdP, etc.).

Note 2: If a male participant was accepted into the trial with a QTcF value that overlaps with values used for grading Grade 1 QTcF prolongation, a TEAE will be reported if the QTcF value is higher than the baseline value.

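### SAP Tables 65/66 count every post-dose QTcF above 450 msec for both sexes with no pre-dose row, although women may enter with QTcF up to 470 msec; the change bands also leave a gap between 59 and 60 msec

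*SAP*

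**What the plan says.** **Entry.** Protocol 8.1.7 states: "To be eligible for participation, the QTcF interval must be within protocol reference range criteria at Screening and Day -2". The reference range, given in Protocol Appendix B Table 4 and SAP Table 6 for men and women in that order, is "≤450 msec • ≤470 msec".

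**Categories.** Protocol 11.4.6.2 introduces its list with "The following criteria will be used to specify noteworthy QTcF intervals". The first entry is "QTcF >450 msec", followed by >480 and >500 msec and by increases of ≥30 and ≥60 msec, with no split by sex. SAP Tables 65/66 turn the first entry into "QTcF >450 - 480 msec" and the smaller increase into "QTcF increase ≥30 – 59 msec from baseline".

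**Layout.** Tables 65/66 have eight rows: 1, 4 and 16 h on Day 1, then 24, 36, 48 and 60 h, and Day 14. There is no pre-dose row. The footnote defines the pre-dose baseline, but only the two increase columns use it.

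**Values analysed.** SAP 4.5.1: "For ECG measurements performed in triplicate, the mean of the replicates will be used for analysis, including analyses of change from baseline". SAP 3.3.3 applies the same averaging to the baseline.

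**The concern.** The secondary ECG endpoint in SAP 3.2 is the frequency of changes from baseline. SAP 4.2 confirms that there is no control group, so each participant's own pre-dose value is the main reference. The absolute QTcF columns leave that reference out, and for women the lowest cut-off lies inside the range in which they may enter.

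The neighbouring displays are built differently. Tables 59/60 use the sex-specific grades of SAP Table 6 and carry a baseline row. Tables 67/68 require a change of more than 25% as well as an absolute limit for PR, QRS and heart rate. Tables 65/66 do neither for the absolute QTcF columns, so a pre-existing value can appear there as a post-dose finding, and the two QTcF displays can disagree about the same woman.

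**Working it through.** The plan states no figure to reproduce here. The check applies the two sets of rules to the same values and then gives a sense of scale.

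**1. Rules applied to example values**

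| Participant | Pre-dose → post-dose (msec) | Tables 65/66 absolute column | Grade, Tables 59/60 |
|---|---|---|---|
| Woman | 450 → 450 | not counted | none |
| Woman | 451 → 451 | >450 to 480 | none |
| Woman | 460 → 460 | >450 to 480 | none |
| Woman | 470 → 470 | >450 to 480 | none |
| Woman | 465 → 452 | >450 to 480 | none |
| Man | 450 → 450 | not counted | none |

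The affected band is women above 450 and up to 470 msec. A woman whose value falls but stays above 450 is still counted. One such woman is 1/20 = 5% of a row if all 20 have a reading, or 1/16 = 6.25% if Cohort T5 is not enrolled.

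**2. How many women might enter in that band** (assumed inputs)

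The documents give no QTcF distribution and no number of women. Assume a normal entry value with mean *m* and SD *s*, truncated at 470:

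p = [Φ((470−m)/s) − Φ((450−m)/s)] / Φ((470−m)/s)

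- m = 410, s = 15: p = 0.004
- m = 420, s = 15: p = 0.022
- m = 420, s = 20: p = 0.061
- m = 430, s = 20: p = 0.139

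With 10 women (assumed), the expected number over this range is 0.04 to 1.39. The chance of at least one, 1 − (1 − p)^10, is 4% to 78%. The range is wide because it rests on the assumed mean and SD.

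**3. How often such a woman is counted** (assumed noise)

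Take a timepoint SD of 6 and a replicate SD of 5 msec. A single reading then has SD √(36 + 25) = 7.81, and a triplicate mean √(36 + 25/3) = 6.66. At a true QTcF of 455, P(>450) is Φ(5/7.81) = 0.739 and Φ(5/6.66) = 0.774. Over three triplicate and five single timepoints the average is (3 × 0.774 + 5 × 0.739)/8 = 0.75. With SDs of 8 and 6 it is 0.70. At a true value of 460 the two figures are 0.91 and 0.85.

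**4. Are most counts pre-existing values?** (assumed inputs)

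A no-effect simulation applied eligibility at two single ECGs, with women's mean 415–425, between-subject SD 15 and the noise ranges above. At least one of eight post-dose readings exceeded 450 in 6% to 23% of women. Requiring a pre-dose baseline at or below 450 left about 4.5% to 17%, so 69% to 82% of the women counted had a baseline at or below 450. The rate per reading, which is what a table row shows, was 1.7% to 7.2%. For men (mean 400–410) it was at most 0.7%.

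**5. The gap in the change bands**

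Pre-dose triplicate 400, 401, 401 gives a mean of 1202/3 = 400.67. A single post-dose reading of 460 is an increase of 59.33 msec, which is above 59 and below 60. It falls in neither SAP column. Under Protocol 11.4.6.2 it meets ≥30 and there is no gap.

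**The case against.** The strongest reply is that the information is already in the report. Tables 59/60 categorise QTcF by sex-specific grade with baseline and maximum post-baseline rows. Tables 61/62 give baseline and change with 90% confidence intervals. Listing 19 gives sex, each reading and both changes for every participant. Within Table 65 itself, a woman steady at 460 appears in the absolute column and in neither increase column. There are 20 participants and no hypothesis test. All of this stands and limits the weight of the point. It does not make Tables 65/66 readable on their own: each row is a count per column, so the person counted cannot be linked to her baseline there.

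Four stronger readings are tempting, and the documents do not support them.

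- A reader might infer that Tables 65/66 are the only categorical view of QTcF. Tables 59/60 are another.
- A reader might infer that men at their entry limit are affected. The cut is strictly above 450, so an unchanged man at 450 is not counted. Note 2 to Protocol Table 4 and SAP Table 6 does envisage a man accepted in the Grade 1 range, which conflicts with Protocol 8.1.7; those passages need to be reconciled.
- A reader might infer that the >450 counts would consist mainly of values carried over from entry. Step 4 points the other way under its assumptions: most of the women counted had a baseline at or below 450 and crossed the cut by ordinary fluctuation.
- A reader might infer that the cut should be replaced by 470 for women, or that only newly raised values should be counted. The first departs from the protocol's prespecified criterion. The second would drop a woman rising from 452 to 478 from every Table 65 column, since she starts above the cut and her rise of 26 msec is under 30.

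The band gap is also unlikely to matter in practice. It is still a literal mismatch with the protocol.

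**Conclusion.** The point holds and is minor. As laid out, Tables 65/66 cannot distinguish a woman who entered above 450 msec from one who rose above it after dosing, and they can disagree with Tables 59/60 about the same woman. This follows from the text alone. Its size does not: every rate in steps 2 to 4 rests on assumed QTcF means, SDs and, in step 2, numbers of women. What can be said without those assumptions is that one such woman makes up 5% of a full row of 20. No primary PK endpoint and no test is affected. The gap between 59 and 60 msec is a separate wording error, certain in form and rare in effect.

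**What to change.** In the shells of SAP Tables 65/66:

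1. Keep the protocol's >450, >480 and >500 msec categories.
2. Add a pre-dose baseline row.
3. Show the >450 column separately for men and women.
4. Optionally, add the number of participants newly above the cut (pre-dose baseline at or below it) beside the full count, not in place of it.
5. Write the change bands as ≥30 to <60 and ≥60 msec, consistent with Protocol 11.4.6.2.

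The cost is shell wording and a few lines of code. No new data and no protocol change are needed. Items 2 to 4 leave the full post-dose counts as they are and show which were present before dosing; item 5 only assigns increases between 59 and 60 msec to the lower band.

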## Table 66: Categorical Summary of QTcF Interval by Timepoint – Safety Subset Population

х

x(xx)

		PR Interval, QRS Duration, and RR Interval Category								
TT	N	PR change from baseline >25% increase resulting in PR >200 msec	QRS change from baseline >25% increase resulting in QRS >120 msec	HR change from baseline >25% decrease resulting in HR <50 bpm	HR change from baseline >25% increase resulting in HR >100 bpm					
Timepoint	N	n (%)	n (%)	n (%)	n (%)					
Day 1, 1 h Post-Dose	х	x (xx)	x (xx)	x (xx)	x (xx)					
Day 1, 4 h Post-Dose	х	x (xx)	x (xx)	x (xx)	x (xx)					
Day 1, 16 h Post-Dose	х	x (xx)	x (xx)	x (xx)	x (xx)					
Day 2, 24 h Post-Dose	x	x (xx)	x (xx)	x (xx)	x (xx)					
Day 2, 36 h Post-Dose	х	x (xx)	x (xx)	x (xx)	x (xx)					
Day 3, 48 h Post-Dose	х	x (xx)	x (xx)	x (xx)	x (xx)					
Day 3, 60 h Post-Dose	х	x (xx)	x (xx)	x (xx)	x (xx)					

# Table 67:Categorical Summary of PR Interval, QRS Duration, and RR Interval by Timepoint –
Safety Population

Notes: N = Number of participants in the Safety Population with ECG measurements assessed at the respective timepoint. n = Number of participants who experienced the event. Participants may be counted in more than one category. Pre-Dose Baseline = The most recent measurement prior to start of infusion.

x(xx)

x(xx)

x(xx)

Table with similar format:

Day 14

# Table 68:Categorical Summary of PR Interval, QRS Duration, and RR Interval by Timepoint –
Safety Subset Population

#### 14.3.8 Displays of Audiology Results

### Table 69: Ear Otoscopy Result, Post-Dose Compared to Baseline by Timepoint and Ear – Safety Population

[Implementation Note: If there are no problems at baseline (blockage of wax or foreign body or any problem other than wax or foreign body), only keep the "No Apparent Problem" rows.]

				Post-Baseline Result						
				No Apparent Problem		Blockage of Wax or Foreign Body		Any Problem Other than Wax or Foreign Body		
Ear	Time Point	Baseline Result	Ν	n	%	n	%	n	%	
Right	Day 3	No Apparent Problem	Х	х	XX	Х	XX	х	XX	
		Blockage of Wax or Foreign Body	Х	х	XX	Х	XX	х	XX	
		Any Problem Other than Wax or Foreign Body	Х	х	XX	Х	XX	х	XX	
	Day 14	No Apparent Problem	Х	х	XX	Х	xx	х	XX	
		Blockage of Wax or Foreign Body	Х	х	XX	Х	xx	х	XX	
		Any Problem Other than Wax or Foreign Body	Х	х	XX	Х	xx	х	XX	
	Day 30	No Apparent Problem	Х	х	XX	Х	xx	х	XX	
			Х	х	XX	Х	XX	х	XX	
Left	Day 3	No Apparent Problem	Х	х	XX	Х	XX	х	XX	
			Х	х	XX	Х	XX	х	XX	
	Day 14	No Apparent Problem	Х	х	XX	Х	XX	х	XX	
			Х	х	XX	Х	xx	х	XX	
	Day 30	No Apparent Problem	Х	х	XX	Х	XX	х	XX	
			Х	х	XX	Х	XX	х	XX	
Notes: $N = N$	umber of participants in the	e Safety Population with ear otoscopy results at the re-	spective timepoin	nt. Baseline = 7	The most recen	t measurement	prior to start o	f infusion.	.	

Table with similar format:

 Table 70:
 Ear Otoscopy Result, Post-Dose Compared to Baseline by Timepoint and Ear – Safety Subset Population

### Table 71: Pure-Tone Audiometry Toxicity Grade by Timepoint and Severity – Safety Population

[Implementation Note: If there is not at least one mild, moderate, or severe result, then only the "Baseline" and "Maximum Severity Post Baseline" rows will be shown for that parameter.]

		Any Graded Event		Mild / Grade 1		Moderate/ Grade 2		Severe/ Grade 3	
Time Point	Ν	n	%	n	%	n	%	n	%
Baseline	х	х	XX	х	XX	х	XX	х	XX
Maximum Severity Post Baseline	х	х	XX	х	xx	х	xx	х	XX
Day 3	х	х	XX	х	xx	х	xx	х	XX
Day 14	х	х	XX	х	xx	х	xx	х	XX
Day 30	х	х	XX	х	xx	х	xx	х	XX
Notes: $N = Number of participants in the$	Safety Popul	lation with r	ure-tone au	diometry a	ssessed at th	e respectiv	e timenoint	Baseline =	The most

Notes: N = Number of participants in the Safety Population with pure-tone audiometry assessed at the respective timepoint. Baseline = The most recent measurement prior to start of infusion. The "Maximum Severity Post Baseline" rows indicate the maximum severity experienced by each participant at any time point post baseline, including unscheduled assessments.

Table with similar format:

Table 72:Pure-Tone Audiometry Toxicity Grade by Timepoint and Severity – Safety Subset
Population

Table 73:	Pure-Tone Audiometry Threshold Measurement and Change from Baseline by Timepoint, Frequency, and Ear – Safety
	Population

					Measure	ment (dB)		Change from Baseline (dB)				
Ear	Timepoint	Frequency (kHz)	Ν	Mean	SD	Median	Min, Max	Mean	SD	Median	Min, Max	
Right	Baseline	0.5	Х	XX.X	XX.X	xx.x	xx, xx	-	-	-	-	
		1.0	Х	XX.X	XX.X	xx.x	xx, xx	-	-	-	-	
		2.0	Х	XX.X	XX.X	xx.x	xx, xx	-	-	-	-	
		4.0	Х	XX.X	XX.X	xx.x	xx, xx	-	-	-	-	
		6.0	Х	XX.X	XX.X	XX.X	xx, xx	-	-	-	-	
		8.0	Х	XX.X	XX.X	xx.x	xx, xx	-	-	-	-	
		9.0	Х	XX.X	XX.X	XX.X	xx, xx	-	-	-	-	
		10.0	Х	XX.X	XX.X	xx.x	xx, xx	-	-	-	-	
		11.0	Х	XX.X	XX.X	xx.x	xx, xx	-	-	-	-	
		12.5	Х	XX.X	XX.X	XX.X	xx, xx	-	-	-	-	
		14.5	Х	XX.X	XX.X	xx.x	xx, xx	-	-	-	-	
		16.0	Х	XX.X	XX.X	xx.x	xx, xx	-	-	-	-	
		18.0	Х	XX.X	XX.X	XX.X	xx, xx	-	-	-	-	
		20.0	Х	XX.X	XX.X	XX.X	xx, xx	-	-	-	-	
	Day 3	0.5	Х	XX.X	XX.X	XX.X	xx, xx	XX.X	XX.X	XX.X	xx, xx	
		1.0	Х	XX.X	XX.X	XX.X	xx, xx	XX.X	XX.X	XX.X	xx, xx	
	Day 14	0.5	Х	XX.X	XX.X	xx.x	xx, xx	XX.X	XX.X	XX.X	xx, xx	
			Х	XX.X	XX.X	xx.x	xx, xx	XX.X	XX.X	XX.X	xx, xx	
	Day 30	0.5	Х	XX.X	XX.X	XX.X	xx, xx	XX.X	XX.X	XX.X	xx, xx	
			Х	XX.X	XX.X	xx.x	xx, xx	XX.X	xx.x	XX.X	xx, xx	
Left	Baseline	0.5	Х	XX.X	XX.X	xx.x	xx, xx	-	-	-	-	
			Х	XX.X	XX.X	XX.X	xx, xx	-	-	-	-	
Notes: $N = Nu$ infusion.	imber of participants in the S	Safety Population with the	pure-tone au	liometry assess	sed at the respec	ctive timepoint	and frequency. I	Baseline = Th	e most recent n	neasurement p	rior to start of	

Table with similar format:

Table 74:Pure-Tone Audiometry Threshold Measurement and Change from Baseline by Timepoint, Frequency, and Ear – Safety Subset
Population

				Measurement (dB)				Change from Baseline (dB)				
Ear	Timepoint	Frequency (kHz)	Ν	Mean	SD	Median	Min, Max	Mean	SD	Median	Min, Max	
Right	Baseline	1.5	х	XX.X	XX.X	XX.X	xx, xx	-	-	-	-	
		2.0	Х	XX.X	XX.X	XX.X	xx, xx	-	-	-	-	
		3.0	Х	XX.X	XX.X	XX.X	xx, xx	-	-	-	-	
		4.0	х	XX.X	XX.X	XX.X	xx, xx	-	-	-	-	
		6.0	х	XX.X	XX.X	XX.X	xx, xx	-	-	-	-	
	Day 3	1.5	х	XX.X	XX.X	XX.X	xx, xx	XX.X	XX.X	XX.X	xx, xx	
			х	XX.X	XX.X	XX.X	xx, xx	XX.X	XX.X	XX.X	xx, xx	
	Day 14	1.5	х	XX.X	XX.X	XX.X	xx, xx	XX.X	XX.X	XX.X	xx, xx	
			х	XX.X	XX.X	XX.X	xx, xx	XX.X	XX.X	XX.X	xx, xx	
	Day 30	1.5	х	XX.X	XX.X	XX.X	xx, xx	XX.X	XX.X	XX.X	xx, xx	
			х	XX.X	XX.X	XX.X	xx, xx	XX.X	XX.X	XX.X	xx, xx	
Left	Baseline	1.5	х	XX.X	XX.X	XX.X	xx, xx	-	-	-	-	
			х	XX.X	XX.X	XX.X	xx, xx	-	-	-	-	
Notes: N = Nur	nber of participants in the Saf	ety Population with th	e DPAOEs a	ssessed at the re	spective timepo	int and frequen	cy. Baseline = T	he most recen	t measurement	prior to start of	of infusion.	

